2.4.5 Subgroup Analyses

In order to investigate the homogeneity of the results of the analyses of the primary endpoint, as well as the first secondary endpoint, across different subgroups, the following factors will be used for definition of subgroups: injection tool (needle, cannula, and combination), study site, FST (I-III and IV-VI), race, ethnicity, gender, age group (\leq median age and $>$ median age), and total injection volume group (\leq median total injection volume and $>$ median total injection volume). Pooling of subgroup categories may be needed based on observed data. The no treatment control group subjects will be pooled across all study sites for the injection tool and injection volume subgroup analyses.

For the primary endpoint, Fisher’s exact tests will be used for comparison of responder rates, as well as confidence intervals of the differences in responder rates within each subgroup. These will be displayed in graphs.

If the primary effectiveness analysis is stratified by injection tool, the subgroup tables will also be stratified, although interpretation should be cautious given sample sizes may be small.

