10.6 Subgroup analyses

10.6.1 Effectiveness

In order to investigate the homogeneity of the results of the analyses of the primary endpoint, as well as the first secondary endpoint, across different subgroups, the following factors will be used for definition of subgroups, respectively:

- Injection tool (needle, cannula, and combination)
- Study site
- Fitzpatrick skin types (I-III and IV-VI)
- Race
- Ethnicity
- Gender
- Age (\leq median age vs $>$ median age)
- Injection volume (\leq median total injection volume vs $>$ median total injection volume)

Fisher's exact tests will be used for comparison of responder rates, as well as confidence intervals of the differences in responder rates within each subgroup. These will be displayed in graphs.

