1.1.2 Number of Subjects and Randomization

Approximately 224 subjects will be randomized (3:1) to either a GP0109 treatment group or to a no treatment control group. At least 45 subjects will be Fitzpatrick skin type (FST) IV through VI. This includes at least 23 subjects with FST V-VI, where at least 12 subjects will be FST V and at least 11 subjects will be FST VI.

Approximately 15 sites are planned for the study, with approximately 5 sites using needle for injection, approximately 5 using cannula for injection, and approximately 5 with a combination of needle and cannula for injection. The aim is to achieve an even distribution of subjects between the assigned sites.

In the GP0109 treatment group, approximately 56 subjects will receive injection with needle, 56 with cannula, and 56 with both needle and cannula combined. Approximately 56 subjects will be randomized to a no treatment control group at baseline.

Details of the enrollment to be conducted in two stages follow:

- Stage 1: will include the first approximately 50 eligible subjects randomized. At least 10 of these subjects will be FST IV-VI, where at least 3 subjects will be FST V and at least 2 subjects will be FST VI. The aim is to achieve an even distribution of subjects to a minimum 1 site using needle for injection, 1 site with cannula for injection, and 1 site with combination of needle and cannula for injection.
- Stage 2: will include approximately 174 eligible subjects.

The subject randomization list for each stage will be stratified by injection tool (needle, cannula, and combination) and FST group (FST I-III, FST IV, and FST V-VI). The FST I-III group only will be further stratified by study site. Study sites are assigned in advance to 1 of the 3 injection tool categories.

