2.4.3 Primary Effectiveness Analysis

Responder rate based on the GJS, as assessed live by the Blinded Evaluator at 3 months after baseline, will be the primary effectiveness endpoint. A responder will be defined as a subject with at least 1 grade improvement from baseline on both sides of the face concurrently.

The null hypothesis will be that there is no relationship between responder rate and treatment group (i.e., the responder rate is the same in treated and untreated subjects). The alternative hypothesis will be that there is a relationship between responder rate and treatment group (i.e., the responder rate is different in treated subjects compared to untreated subjects).

[figure not shown]
The estimates of the responder rate in each treatment group will be presented as well as the difference in responder rates. Corresponding confidence intervals for responder rates (via Clopper-Pearson) and the difference in responder rates (via normal approximation) along with the p-value (via Fisher's exact test) for the difference will also be presented.

First, the Breslow-Day test for homogeneity of odds ratios will be used to assess consistency of GJS odds ratios across all injection tool strata (the needle-treated group, the cannula-treated group,

[figure not shown]

and the combination group). A significance level of 0.05 will be used to determine if the responder rates are non-homogenous. If the Breslow-Day p-value is less than or equal to 0.05, the primary analysis will be stratified (i.e., conducted separately) for the needle-treated group, the cannula-treated group, and the combination group, using a significance level of 1.7% to account for multiplicity. If the Breslow-Day p-value is greater than 0.05, the analysis will be carried out on pooled groups, using a significance level of 5%. Regardless of whether the primary analysis will be based on pooled injection tool groups, or done separately, the no treatment control group subjects will be pooled across all study sites. In either case, the primary analysis will be repeated in each injection tool stratum as part of the pre-planned subgroup analyses (see SAP Section 2.4.5).

In order to assess the poolability of study sites, a Breslow-Day test for homogeneity of odds ratios across sites will be performed. Regardless of results, the primary analysis will be repeated for each study site as part of the pre-planned subgroup analyses (see SAP Section 2.4.5).

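### The plan sets out to examine consistency of effect across skin type, race, ethnicity, gender and age but includes no between-subgroup contrast for these factors, only within-subgroup tests and intervals whose significance depends largely on subgroup size

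*SAP*

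**What the plan says.** SAP section 2.4.5 gives the purpose of the subgroup analyses: "In order to investigate the homogeneity of the results of the analyses of the primary endpoint". The factors are injection tool, study site, FST (I-III and IV-VI), race, ethnicity, gender, age split at the median and total injection volume split at the median. For the primary endpoint the method is Fisher "exact tests will be used for comparison of responder rates, as well as confidence intervals of the differences in responder rates within each subgroup", displayed in graphs. Protocol section 10.6.1 has the same purpose and the same method ("exact tests will be used for comparison of responder rates").

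Two of these factors also have a between-subgroup test, in SAP 2.4.3. For injection tool: "First, the Breslow-Day test for homogeneity of odds ratios will be used to assess consistency of GJS odds ratios across all injection tool strata". For site: "In order to assess the poolability of study sites, a Breslow-Day test for homogeneity of odds ratios across sites will be performed". Protocol section 10.4.1 plans both as well.

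Neither document names an interaction test, homogeneity test or contrast for FST, race, ethnicity, gender or age. Neither says how consistency is to be concluded for them.

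**The concern.** A Fisher test inside a subgroup asks whether treated and control subjects differ in that subgroup. Homogeneity asks whether that difference varies from one subgroup to another. A small subgroup with the full effect will often be non-significant. Two significant subgroups can have quite different effects. So the stated question is not answered by the stated test.

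Skin type is where this matters most, because the trial sets an enrolment floor for it ("At least 45 subjects will be Fitzpatrick skin type (FST) IV through VI") and the darker skin types form the smaller group. A non-significant FST IV-VI row beside a highly significant FST I-III row could be taken to mean that the device works less well in darker skin, when the two rows differ only in size.

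**Working it through.** **Inputs.**
- Total and allocation: "Approximately 224 subjects will be randomized (3:1) to either a GP0109 treatment group" (SAP 1.1.2).
- FST IV-VI floor of 45 (SAP 1.1.2). Randomization is "stratified by injection tool (needle, cannula, and combination) and FST group (FST I-III, FST IV, and FST V-VI"), so 3:1 should roughly hold within FST IV-VI: 45 × 0.75 ≈ 34 treated and 11 control. The remainder is 168 − 34 = 134 treated and 56 − 11 = 45 control in FST I-III.
- Responder rates 70% and 32% (SAP 2.7.3).
- Two-sided 5% level by default (SAP 2.1.2).
- About 10% dropout at month 3 (SAP 2.7.4). Baseline observation carried forward (SAP 2.4.2) makes a missing subject a non-responder. If 10% are missing in each arm, the rates become 0.9 × 70% = 63% and 0.9 × 32% = 28.8%.
- Age half: 168/2 = 84 treated and 56/2 = 28 control. Age is not a stratification factor, so this is an expected split.

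**Method.** Exact power of the two-sided Fisher test: sum Bin(x; n₁, p₁) × Bin(y; n₂, p₂) over all outcomes (x, y) with Fisher p ≤ α.

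**The plan's own figures (SAP 2.7.4).** 150 vs 50 at 5% gives 99.7% (stated: more than 99%). 50 vs 50 at 1.7% gives 91.8% (stated: approximately 90%). Both are reproduced.

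**Probability that the within-subgroup Fisher test is non-significant when the effect is identical everywhere:**

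| Subgroup (treated:control) | 70% vs 32% | 63% vs 28.8% |
|---|---|---|
| FST I-III (134:45) | 0.6% | 2.2% |
| Age half (84:28) | 6.0% | 11.5% |
| FST IV-VI at its floor (34:11) | 43.2% | 53.1% |
| FST IV-VI above its floor (45:15) | 32.3% | 42.5% |
| FST IV-VI above its floor (60:20) | 18.7% | 27.7% |

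If the 45 split differently, from 32:13 to 36:9, the floor figures run 36-51% and 47-64%.

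**What a direct test would do.** In 4,000 simulated trials (134:45 and 34:11) with the same 70% vs 32% in both groups, Breslow-Day signalled a difference in about 5%. With no effect at all in FST IV-VI (32% vs 32%), it signalled one in about 50%.

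**Precision of the contrast.** For the difference between the two risk differences at the planning rates:

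SE = √(0.21/34 + 0.2176/11 + 0.21/134 + 0.2176/45) = √0.03236 ≈ 0.180,

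where 0.21 = 0.70 × 0.30 and 0.2176 = 0.32 × 0.68. The 95% interval is therefore about ±1.96 × 0.180 ≈ ±35 percentage points.

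**The case against.** **The documents do not judge consistency by p-values.** This is right. A reader might infer that a non-significant row would count as inconsistent, but no such rule exists. Intervals are planned and graphed too, and they are a reasonable basis for reading consistency. With normal-approximation intervals (named in SAP 2.4.3 for the primary difference; 2.4.5 names no method), the two FST intervals overlap in about 98% of trials under an identical effect. The FST IV-VI estimate favours treatment in 98-99%. This softens the point but does not remove it. Separate intervals are not a contrast. At 34:11 the FST IV-VI interval still includes zero in 35-41% of trials, and in a further 8-12% it excludes zero while the Fisher test is non-significant.

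**Site.** A reader might add site to the list, because a site of about 11:4 is non-significant 83% of the time. The documents do not support that: site has its own Breslow-Day test, and the per-site Fisher tests are additional.

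**The 43-53% is conditional.** It applies to one factor, with enrolment stopping at a minimum, and at planning rates that the SAP gives as a lower bound for GP0109 and an upper bound for control. At 34:11 with 75% vs 25% the figure is 17%.

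**The remedy is weak.** With about 50% power against complete absence of effect in FST IV-VI, a homogeneity test could replace false alarm with false reassurance. This stands, and the fix has to say so.

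**The primary conclusion is untouched, and supportive analyses can be added later without an SAP amendment (SAP 2.1 and 2.1.2).** Both are true. A contrast specified before the data are seen is still more credible than one added afterwards.

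**Conclusion.** The point holds as a gap in the plan. For FST, race, ethnicity, gender and age the stated aim is homogeneity, and no planned analysis estimates or tests a difference in effect between subgroups. The within-subgroup p-values cannot fill that gap. Under an identical effect the FST IV-VI test is non-significant 43-53% of the time at the floor of 45, against 1-2% for FST I-III and 6-12% for an age half.

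Those figures rest on a split near 34:11 and the planning rates, and the upper ends on 10% missing in each arm counted as non-response. The FST IV-VI figure falls to 32-43% at 45:15 and 19-28% at 60:20.

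It would go too far to say that the plan declares a subgroup inconsistent when its p-value is non-significant, or that the primary inference is affected. The primary test, its significance levels and the injection-tool decision do not depend on these rows. The change is worth making before the analysis is run but is not critical to the trial's main result.

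**What to change.** In SAP 2.4.5, for FST, race, ethnicity, gender and age:

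1. Add the between-subgroup contrast of the treatment effect (difference of risk differences or ratio of odds ratios) with its 95% confidence interval.
2. Add a homogeneity test, such as the Breslow-Day test already specified for tool and site. Pool sparse categories, as 2.4.5 already permits.
3. State that conclusions on consistency rest on the contrast and the subgroup intervals, not on which within-subgroup p-values are significant. The Fisher p-values can stay as descriptive output; removing them is optional.
4. State that the contrast is imprecise and that a non-significant homogeneity test does not establish consistency.

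Leave injection volume out: untreated controls have no volume, and 2.4.5 pools them for that comparison.

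The cost is a few lines of SAP text and one extra column per subgroup table. No new data are needed, and neither the sample size nor the primary analysis changes.

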2.5 Safety Analysis

Safety endpoints will be summarized using descriptive statistics by treatment group based on the Safety population using observed cases. There are no planned inferential statistical analyses of safety endpoints.

2.5.1 Treatment Administration, Post-injection Procedures, and Procedural Anesthetics

Treatment administration endpoints will be summarized for each treatment session (initial, optional touch-up, and optional re-treatment) by treatment area, including injection method, depth of injection, needle size, cannula size, and introducer needle for cannula.

The number of subjects with any post-injection procedures and procedural anesthetics will be summarized by type.

Injection volume will be summarized for each treatment session (initial, optional touch-up, initial + touch-up, optional re-treatment) and overall by treatment area.

2.5.2 Adverse Events (AEs)

All AEs will be summarized relative to treatment session timing using the following categories:

- No Treatment at Baseline: For subjects who receive no treatment at baseline, include AEs before any optional GP0109 treatment at Month 12.
- Initial Treatment with GP0109: Pool AEs for the following (whether optional touch-up treatment received or not):
 - For subjects treated with GP0109 at baseline:
 - include AEs before optional GP0109 re-treatment at Month 12,
 - include AEs through end of study if no re-treatment at Month 12.
 - For subjects who receive no treatment at baseline, include AEs after initial GP0109 treatment at Month 12.
- Re-treatment with GP0109: For subjects treated with GP0109 at baseline, include AEs after optional GP0109 re-treatment at Month 12.

All AEs will be coded according to MedDRA and summarized by System Organ Class (SOC), Preferred Term (PT), and treatment session timing as described above. The number of subjects with at least one event, associated percentage, and number of events will be provided.

For subject counts, a subject will only be counted once per SOC and once per PT in cases where multiple events are reported for a subject within SOC or PT. For event counts, subjects with multiple events in a category will be counted for each event.

The number of subjects with AEs related to study product or study product injection procedure and unrelated AEs, as well as the number of events, will be presented by SOC, PT, and maximum intensity. Action taken for related AEs will also be summarized by SOC and PT using number of events. AEs related to study product or injection procedure with late onset (> 21 days after most recent treatment session) will be listed.

Serious AEs and AEs of special interest (AESIs) will be listed. See Section 8.2.1 of the protocol for a list of visual disturbances considered to be AESIs.

For AEs related to study product or study product injection procedure, the number of days to onset and the duration of event will be summarized by SOC and PT using mean, standard deviation, median, minimum, and maximum. Days to onset of an AE will be derived as the start date minus the date of most recent treatment session. Duration of an AE will be derived as the stop date minus the start date + 1. Missing stop date will not be imputed, and therefore no duration will be calculated in these cases.

In addition, a summary of all AEs will be provided, which will include (but is not limited to):

- number of subjects with at least one AE and number of events (in total as well as serious AEs),
- number of subjects with at least one related AE and number of events (in total as well as serious AEs),
- number of subjects with at least one AESI and number of events,
- number of subjects with at least one unrelated AE and number of events (in total as well as serious AEs),
- number of subjects who did not have an AE.

To evaluate consistency of AEs across different subgroups, related AEs by SOC, PT, and maximum intensity will also be summarized by subgroups, specifically injection tool (needle, cannula, and combination), study site, FST (I-III and IV-VI), race, ethnicity, gender, age group (\leq median age and $>$ median age), and total injection volume group (\leq median total injection volume and $>$ median total injection volume). Pooling of subgroup categories may be needed based on observed data.

CCI

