At the Month 12 visit, subjects in the no treatment control group will be offered optional GP0109 treatment. Subjects in the no treatment control group who do not receive treatment at Month 12 will end the study at Month 12. The subjects who received GP0109 treatment at baseline will also be offered an optional additional treatment at the Month 12 visit if aesthetic improvement is not maintained (as determined by the Treating Investigator and subject). If optional treatment is performed, a 72-hour follow-up telephone call, a 14-day follow up visit, and a 1-month follow-up visit should be scheduled.

GALDERMA EST. 1981	Title 43BBJ1911 - Statistical Analysis Plan - Big Ben Jawline
-----------------------	---

Effectiveness and safety data will be collected for up to 24 months from baseline. Follow-up visits in addition to those mentioned above will occur at 3, 6, 9, 12, 15, 18, 21, and 24 months after baseline. A subject will be involved in the study for up to 25 months, including a 30-day screening period. For subjects in the no treatment control group who do not receive GP0109 treatment at Month 12, the clinical study participation will be approximately 13 months including the screening period. Subjects who receive GP0109 treatment at baseline and decline optional additional treatment at Month 12 will continue to be followed through 24 months after baseline.

Investigator blinding will be accomplished by having a Treating Investigator administer the treatments and having a Blinded Evaluator, to whom randomization and treatment are concealed, conduct blinded assessments. Safety assessments will be performed by non-blinded personnel. The Blinded Evaluator will not be blinded to study treatment following the Month 12 visit. The Sponsor representative(s) will not be blinded during the course of the study.

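### In the final AE tables the GP0109 Initial Treatment column runs to Month 24 for subjects not re-treated, while the No Treatment column stops at Month 12, so crude AE percentages differ without any device effect

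*SAP*

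**What the plan says.** SAP 2.5.2 sorts AEs by treatment-session timing into three columns.

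- **No Treatment at Baseline:** "For subjects who receive no treatment at baseline, include AEs before any optional GP0109 treatment at Month 12". SAP 1.1.1 adds: "Subjects in the no treatment control group who do not receive treatment at Month 12 will end the study at Month 12". This column therefore holds at most about 12 months per subject.
- **Initial Treatment with GP0109:** this pools three sets of follow-up. For baseline-treated subjects who are re-treated, the rule is "include AEs before optional GP0109 re-treatment at Month 12". For those not re-treated, it is "include AEs through end of study if no re-treatment at Month 12"; SAP 1.1.1 says that subjects who "decline optional additional treatment at Month 12 will continue to be followed through 24 months after baseline". The third set is the crossed-over controls: "For subjects who receive no treatment at baseline, include AEs after initial GP0109 treatment at Month 12".
- **Re-treatment with GP0109:** events after the optional Month 12 session in baseline-treated subjects, so about 12 months.

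The statistics are crude: "The number of subjects with at least one event, associated percentage, and number of events will be provided". The overview table covers all, related, unrelated and serious AEs and AEs of special interest (AESIs). Protocol 10.5 uses the same split into no treatment, first treatment and second treatment. On inference, SAP 2.5 states: "There are no planned inferential statistical analyses of safety endpoints". SAP 2.6 and protocol 10.8 also plan an analysis of 12-month data for all subjects. Protocol 9.6 gives that analysis its own interim report.

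**The concern.** A percentage with at least one AE rises with time observed, and so does an event count. Placing a 12-month column beside one that runs to 24 months for some subjects builds in a difference unrelated to the device. How long a GP0109 subject counts under Initial Treatment also depends on a choice made after randomisation, because re-treatment is offered when improvement has not been maintained. Controls treated at Month 12 appear under both No Treatment and Initial Treatment, so the two columns are not the randomised groups.

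The counts most exposed are those for which a control column is most informative: all-cause, unrelated and serious AEs, and AESIs. Protocol 8.11.3 counts AESIs whatever their cause, including a one-line Snellen loss. By the schedule of events, a control has post-baseline visual tests at Visits 3 to 7, which is five visits. A GP0109 subject with no touch-up and no re-treatment has them at Visits 2b, 3 to 7 and 8 to 11, which is ten, plus the post-injection test on Day 1. Chance one-line losses have more opportunities to enter the GP0109 column.

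The same windows affect Initial Treatment against Re-treatment. There the distortion makes repeat treatment look relatively safer.

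**Working it through.** **The plan's own safety figure.** SAP 2.7.5 gives about 80% probability of seeing at least one AE of 1% incidence in 168 treated subjects. 1 − 0.99^168 = 0.815, so the figure reproduces. It does not depend on the column windows and does not settle this point.

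**Inputs from the documents.** 168 GP0109 and 56 control subjects (SAP 2.7.1). Windows: 12 months for No Treatment, 12 months for re-treated GP0109, 24 months for GP0109 not re-treated, and about 12 months for crossed-over controls (SAP 1.1.1 and 2.5.2).

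**Assumptions, not in the documents.** The AE hazard is constant and identical with and without device, and there is no dropout. The 12-month incidence is p = 30%. K = 40 of the 56 controls are treated at Month 12. A share f of GP0109 subjects is not re-treated.

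**Formulas.** 24-month incidence = 1 − (1 − p)² = 1 − 0.7² = 51%.

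Initial Treatment column = [168·f·0.51 + 168·(1 − f)·0.30 + 40·0.30] / (168 + 40).

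| f | Sum / 208 | Initial Treatment | No Treatment | Excess |
|---|---|---|---|---|
| 0% | (50.40 + 12) / 208 | 30.0% | 30.0% | 0 |
| 25% | (21.42 + 37.80 + 12) / 208 | 34.2% | 30.0% | +4.2 points |
| 50% | (42.84 + 25.20 + 12) / 208 | 38.5% | 30.0% | +8.5 points |
| 75% | (64.26 + 12.60 + 12) / 208 | 42.7% | 30.0% | +12.7 points |

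**Source of the excess.** The excess equals (0.51 − 0.30)·168·f / (168 + K). It is driven by f alone, and K appears only in the denominator. At f = 50% with no crossed-over controls, the column would be 0.5·51% + 0.5·30% = 40.5%. Adding the 40 controls lowers it to 38.5%.

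**Re-treatment column.** With the same hazard over about 12 months it shows 30.0%, against 38.5% for Initial Treatment at f = 50%.

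**Event counts.** At f = 50%, mean follow-up in Initial Treatment is (84·12 + 84·24 + 40·12) / 208 = 3504 / 208 = 16.8 months. Events per subject would be 16.8 / 12 = 1.40 times those under No Treatment.

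**Other incidences.** With half not re-treated and 80% of controls crossing over, Initial Treatment shows 13.6% against 10%, 26.3% against 20%, and 49.5% against 40%. The ratios are 1.36, 1.32 and 1.24.

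**Equal windows.** If both randomised groups are cut at Month 12, the two percentages agree under this model.

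**The case against.** The strongest reply is that the plan already contains a largely time-matched view. The 12-month analysis covers both stages and supports the early regulatory submission. At that cut both randomised groups have about 12 months, and time after crossover or re-treatment is mostly absent. This stands, and it confines the problem to the final 24-month tables. What remains is that the 12-month analysis describes its data only as running up to that timepoint, without an explicit AE cut-off for each subject.

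The safety analysis is descriptive, with columns defined by treatment session. This also stands. A reader might infer an inflated type I error or a biased safety decision, but there is no test, threshold or decision rule to distort. Even so, percentages printed side by side will be read as a comparison.

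A reader might also infer that pooling crossed-over controls causes the excess. It does not: each contributes about 12 months, the same as the No Treatment window, so they reduce it. Their double membership is a separate fault of presentation.

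A constant hazard does not describe injection reactions, which protocol 6.5.3 expects typically to resolve within two weeks. Both windows capture such early events, so a claim that related AEs in general are inflated would go too far.

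Finally, AESIs and serious AEs are listed individually, so a reader could place them before or after Month 12. SAP 2.5.4 summarises the other safety assessments by baseline group and visit. The table shells are in a companion document not available here, and SAP 2.5.3 is redacted, although its title concerns expected post-treatment events. These points soften the problem but do not supply a matched AE table.

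**Conclusion.** The point holds for the final AE tables, at moderate severity. The windows are unequal by the SAP's own definitions, and no visible text supplies a common window or an AE table by randomised group for the final analysis. Against control, the distortion overstates GP0109 risk and does not hide it. Against Re-treatment, it flatters the repeat session.

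The size is conditional. The +4.2 to +12.7 points rest on a constant hazard, no dropout, 30% incidence at 12 months, 40 of 56 controls treated at Month 12 and 25% to 75% not re-treated. Under that model the excess vanishes only if every GP0109 subject is re-treated. Dropout after Month 12 would shrink it. The primary endpoint, data collection and trial conduct are untouched.

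**What to change.** In SAP 2.5.2, before database lock:

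1. Add, as the main GP0109 against control AE summary, events with onset from Day 1 to before any optional treatment at the Month 12 visit, by baseline group. State the same AE cut-off for the 12-month analysis in SAP 2.6.
2. Show separately: events after Month 12 in GP0109 subjects not re-treated; events in controls after their first treatment at Month 12; and events after re-treatment.
3. If a pooled first-treatment column is kept, limit it to a fixed 12 months after treatment.

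Exposure-adjusted rates are optional. They also assume a roughly constant hazard, and when events cluster early, longer follow-up dilutes the rate. A Month 12 cut will not fully equalise AESI ascertainment, because treated subjects still have Visit 2b, the post-injection test and any touch-up visits; a footnote can say so.

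The cost is SAP wording and a few extra table columns. No new data are needed, and SAP 2.5.4 already uses baseline-group columns for the other safety assessments.
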